### **11. SPUTUM ANALYSIS**

Summary of sputum collection at V1 (Day 1) and V4 (Month 30) will be provided by arms, including sample type, reason for not collected, and test results.

## **12. IMAGING ANALYSIS**

Only sub-cohort participants are planned to have imaging tests; thus, the analysis defined in this chapter will only perform in Sub-cohort Population.

Imaging analysis is based on quantitative HRCT scanning. The CT scan data collected from the sub-cohort in this study provide information on lung structural damage, and the imaging measures are defined as:

**Table 3 CT Scan Data and Imaging Endpoints**

Imaging Analysis Category	Imaging Measures (Description)
Lung density/Emphysema	Perc15 (Corrected for Lung Volume) LAA-950 (Low Attenuation Area-950) DPM_Emphysema
Airway	Average wall thickness (mm) Airway Wall Area (%) Average of major inner diameter (mm) Average of minor inner diameter (mm) Total Airway Count (TAC) Pi10 (Including Pi10All and Pi10Le20)
Gas Trapping	E/I ratio Air Volume DPM_Airtrap (Gas Trapping)

Summary of imaging measures at baseline and Visit 4 (Month 30) will be provided by arm descriptively with 95% CI. Change from baseline will be provided in a same table.

Summary of imaging measures change with exacerbation will be provided in the COPD patients who had CT scan in exacerbation visits. The analysis will be based on events (exacerbations) instead of on patients, i.e., a same patient with 2 exacerbation imaging tests will be analysis as 2 records. Descriptive summary of baseline, exacerbation and the end of study (Visit 4 or early withdrawal) will be provided with 95% CI. Exacerbation visit change from baseline, end of study change compared with exacerbation visit will be provided in a same table with covariates of age, sex and height at baseline.

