## 5.4. Scientific Rationale for Study Design

To reflect the real-world management and patient outcomes of COPD in China, a non-drug interventional study design was chosen. Patient diagnosis and treatment will be left to their physicians' judgement and routine practice. This study will not provide or recommend any treatment. By capturing the prospective and longitudinal patient-level data in a real-world clinical setting, the study will fulfil the needs to understand the phenotypes and their disease progression, and current disease management more comprehensively and in depth. Study results will inform clinical practice and may improve patient outcomes.

This study will use COPD and non-COPD cohorts to provide cross-sectional and longitudinal data on multiple clinical, radiological and biological evaluations. Study participants will mostly represent mild to moderate airflow limitation grades of COPD and symptomatic non-COPD (i.e. chronic bronchitis) populations, whose disease progression is not well understood in China.

Air pollution and increased biomass exposure are likely to be key contributors to the development of COPD in China. Previous nation-wide studies showed a large proportion of COPD patients (20-40%) in China are never smokers. Kurmi et al. reported that 5.4% of never smokers had airflow obstruction (AFO) among Kadoorie cohort [[Kurmi, 2014](#)]. The prevalence of COPD was estimated to be 5.2% among never smokers in Zhong et al [[Zhong, 2007](#)]. This suggested that factors other than smoking (e.g. biomass, occupational exposure, and air pollution) may also play an important role in COPD progression. However, there is a lack of data on phenotypes and disease progression in never smokers with COPD. Differing from the Western cohorts in which participants were required to have at least 10-pack year smoking history, never smokers with diagnoses of COPD or chronic bronchitis (with respiratory symptoms who don't meet the spirometric criteria of COPD) are also recruited. In addition, air pollution data will be collected retrospectively to explore the association between air pollution and COPD natural history.

Healthy subjects who are never smokers and without a diagnosis of respiratory condition and other significant diseases will also be recruited to this study as controls, e.g. providing data on baseline natural lung function decline and lung structural damage in a general population.

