where  $\hat{\sigma}_p^2 = \hat{\sigma}_\beta^2 + 12(P - 1)\hat{\sigma}^2 / [D^2 P(P + 1)]$ ,  $r = N_2/N_1$ , and  $N_1$  and  $N_2$  are the sample sizes associated with each of the two groups.

In this study, it is planned to collect  $P=4$  measurements of  $FEV_1$  over  $D=2.5$  years. One of interest is an estimate of the rate of decline in  $FEV_1$  between subjects GOLD I and II.

Under the above assumptions with 95% confidence and a 25% drop out, the following table gives sample sizes necessary to attain the levels of precision of Gold I vs. Gold II comparison.

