### 10.2.3.1. Main Cohort

- Change from baseline and Rate of decline in FEV1 in millilitres (mL):

Descriptive statistics of FEV1 and change from baseline FEV1 will be reported for baseline and all subsequent visits. The raw mean change from baseline at each visit will be presented graphically.

Rates of decline in FEV1 will be estimated for each type of COPD subjects, overall COPD subjects, chronic bronchitis group and healthy control group.

In order to obtain rate of decline in FEV1, particular from a mixed effects model, a random coefficients model, will be used. FEV1 after baseline will be fitted as the response variable with the proposed selection of predictors including type of subjects (i.e. GOLD I-IV, chronic bronchitis, healthy control), age, gender, smoking status, baseline FEV1, count of COPD exacerbations, site, time on study and type of subjects by time interaction. Participants and time on study will be random effects. Further details will be included in RAP.

Rates of decline in other endpoints may also be estimated in a similar fashion, if warranted.

- Rate of moderate/severe exacerbations:

Exacerbations separated by less than 7 days will be treated as a continuation of the same exacerbation. The exacerbation frequency, type and duration will be summarized using descriptive statistics for Full population.

A generalized linear model assuming the negative binomial distribution will be used to analyze the exacerbations rate among different type of subjects. Additional methods including time to event analysis will be considered as appropriate.

- Change from baseline in CAT score:

CAT score and change from baseline value will be summarized using descriptive statistics for the Full population.

If appropriate, Mixed Models Repeated Measures (MMRM) model will be used to analyze CAT score among different type of subjects.

- Clinically important deterioration (CID) components:

CID will be summarized for Full population using descriptive statistics.

If data permit, generalized linear mixed model will be used to analyze CID among different type of subjects and time to CID will be assessed using time to event models.

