### 10.2.3.2. Sub-cohort

General summary/analysis information for each sub-cohort endpoints are listed as below. More details will be included in RAP.

- EXACT events: the analysis will summarize N of events, their onset, duration and severity. EXACT events will be derived according to the EXACT manual [Leidy, 2013] with any alternative considerations detailed in the RAP.

- E-RS: COPD total and domain scores: each 4-week interval summary/analysis will be done. If data permit, mean weekly scores will be considered for the analysis; this assumption will be tested prior starting data analysis. Relationships between mean E-RS scores and other study variables will be evaluated using a range of analysis of variance and analysis of covariance. Changes from baseline in Total and domain scores at pre-defined time points will be analysed using a mixed model for repeated measures, adjusted for baseline E-RS scores and other key variables.

CCI

- 
- Daily Activity: summary/analysis with appropriate statistics will be done based on the data extracted from wrist band.

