## **Patient Report Outcome (PRO) and Activity (Chapter 9)**

The PROs and activities are not only collected by on site visit, and please refer to Protocol schedule of activities for further details.

CAT at each planned visits, including phone call visits, will be summarised.

EXACT and E-RS are collected for 2 period of 180 days after baseline and Month 18. Summary of these 2 questionnaires will be based on the mean score during baseline (defined as study D1-D7), Month 1-6 (defined as up to 180 days from study D8) and Month 18-24 (defined as up to 180 days from Month 18 visit).

Daily steps collected by wrist band is used to stands for physical activity measures. Daily steps are collected for 2 period of approximately 30 days after baseline and Month 18. Summary of daily steps will be based on the participants mean steps during baseline (defined as study D1-D7), Month 1 (defined as up to 30 days from study D8) and Month 18 (defined as up to 30 days from Month 18 visit).

HRCT data will be summarised at baseline and the end of study. In addition, for participants who had exacerbation visits (a pre-defined special unscheduled visit happened after exacerbation observed), the HRCT data of these visits will be summarised and compared with baseline and the end of study.

[figure not shown]

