## 2.3. Study Design

## 2.4. Statistical Hypotheses / Statistical Analyses

This study is mainly descriptive with no formal inference associated with the study objectives. Nominal P-value may be provided as reference. 2-sided 95% confidence intervals will accompany all effect estimates.

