### Model Specification

- Similar to analyses of change in CAT score with MMRM
- In sub-cohort population.

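### SAP amendment 3 estimates no between-arm difference for HRCT, E-RS or CAT change, and it drops the protocol's E-RS mixed model without declaring it

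*SAP*

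**What the plan says.** **HRCT.** SAP 12 states: "Summary of imaging measures at baseline and Visit 4 (Month 30) will be provided by arm descriptively with 95% CI". Change from baseline goes in the same table. The only imaging display with covariates (age, sex, height) is the exacerbation table, which covers COPD patients and compares visits.

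**E-RS.** SAP 2.2.1 states: "Summary of these 2 questionnaires will be based on the mean score during baseline", followed by two later periods. SAP 9.3 specifies a display for EXACT events only. SAP 2.2 still lists change in E-RS as an endpoint. Protocol 10.2.3.2 says that changes from baseline in total and domain scores "will be analysed using a mixed model for repeated measures, adjusted for baseline E-RS scores and other key variables".

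**CAT.** SAP 9.1 gives a descriptive summary of score and change, with no model. Protocol 10.2.3.1 says, if appropriate: "Mixed Models Repeated Measures (MMRM) model will be used to analyze CAT score among different type of subjects".

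**Appended RAP (amendment 2), section 7.4.1.** CAT and E-RS each have an MMRM with type of subjects by visit and LS mean differences. For the HRCT endpoints the model entry reads: "Similar to analyses of change in CAT score with MMRM".

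**Contrast.** SAP 8.1 gives differences from Healthy Control for FEV1 and FVC, in both the MMRM and the random coefficients model.

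**Purpose of the controls.** Protocol 5.4 recruits healthy participants as controls, for example "providing data on baseline natural lung function decline and lung structural damage in a general population".

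**The concern.** Objective 1 is to evaluate progression in COPD and non-COPD participants by health status and HRCT as well as lung function. A change over 2.5 years within a GOLD arm mixes COPD progression with anything all arms share, such as ageing or drift in measurement. The control arms allow the shared part to be removed, but only if a difference between arms is estimated. The SAP does this for spirometry and not for the other three endpoints.

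The arms are not randomised. Healthy Controls are all never smokers and enter only with a CAT score below 10 (Protocol 6.1), so reading one row of a table against another is confounded and has no interval.

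There is also a disclosure question. SAP 2.1 names the CAT rate of change as moved to post hoc and phenotype analyses as descriptive. It says nothing about the E-RS model. The version-history entry for amendment 3 mentions only the new template and a regrouping of endpoints.

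**Working it through.** **1. The plan's own precision figures.** The only ones are for the FEV1 slope (Protocol 10.1.3).
- sigma_p = sqrt(3.8² + 12×3×233²/(2.5²×4×5)) = 125.1, as stated.
- Half-width for GOLD I versus GOLD II at 525 completers each = 1.96×125.1×sqrt(2/525) = 15.1 mL/year (stated 15).
- 525/0.75 = 700, as stated.
- Width for all COPD = 2×1.96×125.1/sqrt(1275) = 13.7 mL/year, as stated.

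These reproduce. No SD or precision is given for HRCT, E-RS or CAT.

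**2. The planned analyses side by side.**

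| Endpoint | Protocol | Appended RAP 7.4.1 | SAP amendment 3 |
|---|---|---|---|
| FEV1, FVC | Slope model with subject type by time for FEV1; similar for others if warranted | MMRM and slope model | MMRM and slope model, differences vs Healthy Control |
| E-RS | MMRM of change, unconditional | MMRM, arm by visit | Period mean scores; no change score, model or CI |
| CAT | MMRM among subject types, if appropriate | MMRM, arm by visit | Descriptive; no model or CI; by arm not written |
| HRCT | Method redacted | MMRM as for CAT | By-arm summary and change with 95% CI; no difference |

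Only the E-RS row shows an unconditional protocol analysis that is absent from the SAP and from its list of changes. The RAP is not uniform on HRCT: its section 7.2 and model entry call for LS mean comparison, but its Table 4 ticks only summaries.

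**3. Precision the missing contrasts would have.** Half-width in units of the SD of change, h = 1.96×sqrt(1/n1 + 1/n2). Arm sizes are the planned ones (SAP 5.1) × 0.75. The 25% comes from the FEV1 calculation ("Under the above assumptions with 95% confidence and a 25% drop out") and is carried over as an assumption.
- GOLD I 75 vs Healthy 37.5: 1.96×sqrt(0.0133+0.0267) = 0.39 (0.34 with no dropout)
- GOLD III 37.5 vs Healthy 37.5: 0.45
- All sub-cohort COPD 187.5 vs Healthy 37.5: 0.35
- GOLD I 75 vs Chronic Bronchitis 75: 0.32
- CAT, all COPD 1275 vs Healthy 90: 1.96×sqrt(0.00078+0.01111) = 0.21 (0.19 with no dropout)

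**4. Should the HRCT contrast adjust for the baseline value?** Suppose both arms change equally on average, baseline and follow-up have the same variance and correlation r, and the arms differ at baseline by g SD. ANCOVA on baseline then estimates (1−r)g instead of zero. Its standard error is about sqrt(1−r²)×sqrt(1/75 + 1/37 + g²/110). With g = 1 and r = 0.9 (assumed), the estimate is 0.10 and the standard error is 0.436×sqrt(0.0133+0.0270+0.0091) = 0.097. The ratio is 1.03, so the 95% interval excludes zero about 18% of the time. Over g from 0.5 to 2 and r from 0.8 to 0.95, this runs from about 7% to about two thirds. The unadjusted difference in change stays at 5%.

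**5. Smoking adjustment.** At most 25 of the 100 sub-cohort GOLD I participants are planned never smokers. Never smokers only, 18.75 vs 37.5: 1.96×sqrt(0.0533+0.0267) = 0.55 SD.

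**The case against.** The study is declared mainly descriptive with no formal inference. SAP 5.2 counts Healthy Control and Chronic Bronchitis as arms, so their HRCT change and intervals sit beside the COPD rows. Protocol 5.4 asks the controls to supply data, which a by-arm table does; it does not promise subtraction. The CAT model was conditional, the protocol's HRCT method is redacted, and SAP 2.1 lists changes from the protocol, not from the RAP. Even the E-RS sentence names baseline and other key variables, not subject type.

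Most of this stands and narrows the point. A reader might infer that the controls never enter any comparison. They do for FEV1 and FVC, and they appear in the HRCT table. A reader might infer that three protocol commitments were broken. Only the E-RS one can be shown.

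A reader might also compute how often a within-arm interval excludes zero when every arm changes equally, and call that a false-positive rate. It is the chance of detecting a change that really occurred, at a size the documents do not give. It could concern only HRCT, since neither CAT nor E-RS has a planned interval. No sentence in the SAP says that within-arm change will be read as excess over controls.

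The descriptive label does not remove the gap. SAP 2.4 says "2-sided 95% confidence intervals will accompany all effect estimates", but for these endpoints no between-arm effect is estimated for an interval to accompany.

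**Conclusion.** The point holds in a limited form. For HRCT, E-RS and CAT, SAP amendment 3 plans no between-arm estimate, so shared change is separated from COPD change only by eye and without adjustment. What is missing is an estimate; no hypothesis test is being asked for. Dropping the E-RS mixed model of change is an undeclared departure from Protocol 10.2.3.2; the arm-by-visit form of that model comes from the RAP. For CAT and HRCT the case rests on Objective 1, the reason given for recruiting controls, and consistency with spirometry.

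The contrasts would be informative but not sharp: about 0.39 SD of change either side for GOLD I versus Healthy Control in the sub-cohort, and about 0.21 SD for all COPD versus Healthy Control on CAT. Both assume 25% dropout at the planned arm sizes and equal SD across arms, and neither allows for covariates. The size of any ageing effect or drift is not in the documents. This should be corrected, but it does not invalidate the study.

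**What to change.** 1. **SAP 9.3.** Restore the E-RS MMRM from RAP 7.4.1 (total and three subscales) with arm, period and arm by period, keeping the baseline adjustment the protocol commits to. Report differences versus Healthy Control with 95% CIs.
2. **SAP 9.1.** Restore the RAP 7.4.1 CAT MMRM with arm by visit and the same contrasts, or state in SAP 2.1 why it is not appropriate.
3. **SAP 12.** Add the difference in Month 30 HRCT change versus Healthy Control, and versus Chronic Bronchitis, with 95% CI, adjusted for age, sex and height, which section 12 already uses. Because the arms are not randomised, show a baseline-adjusted version only as a sensitivity analysis. Because all Healthy Controls are never smokers, handle smoking through a never-smoker sensitivity analysis only.
4. **SAP 2.1.** Declare any model that stays dropped, with the reason, and state that within-arm change is not evidence of excess progression.

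The baseline caution in step 3 also applies to E-RS and CAT, so the difference in change without the baseline term should be shown beside those models. Keep the descriptive tables.

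The cost is SAP wording and a few models, two of them already written in RAP 7.4.1. No new data are needed. The small downside is visibly wide intervals in the 50-person sub-cohort arms.

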## 2. SCHEDULE OF ACTIVITIES (SOA)

Study participants will be followed up for 2.5 years and a total of 4 clinic visits (baseline, 6, 18, and 30 months) are scheduled for study assessments with a visit window of  $\pm 30$  days (Table 1). Baseline data will be collected at Visit 1. In addition, COPD and chronic bronchitis participants will be contacted by phone on trimonthly basis within  $\pm 7$  days of the planned date to assess the CAT and to collect information on exacerbation rates and COPD medications; healthy controls will be contacted by phone on trimonthly basis within  $\pm 7$  days of the planned date to assess the CAT only. For the 4 clinic visits (V1-V4), all the participants should be clinically stable with no exacerbation or other acute medical event for at least 30 days prior to each scheduled visit.

A subset of participants will receive additional digital and biomarker assessments during the study. If moderate/severe exacerbations are reported by the participants or detected by the investigators during the acute phase of event, the participant will be invited to site hospital for an exacerbation visit. If multiple moderate/severe exacerbations are reported or detected, the participants will be contacted in consecutive manner for an exacerbation visit. The total number of the exacerbation visits should be no more than 2, with an interval of at least 21 days. Please note, for the sub-cohort, the planned clinic visits should be scheduled with an interval of at least 60 days after a completed exacerbation visit. When any participant in the sub-cohort is implemented an exacerbation visit, then his/her next planned clinic visit (V2-V4) should be scheduled at least 60 days after completing this exacerbation visit. In this case, the participant's clinic visit may be scheduled outside of the time window of  $\pm 30$  days, which will not be considered as a Protocol Deviation (for more information please refer to the Protocol Deviation Management Plan [PDMP] for this study).

**Table 1** Time and event table

| Protocol Activity                          | Screen/Baseline |               |               |               | Study visit |   |
|--|-----------------|---------------|---------------|---------------|-------------|---|
|  | V1              | V2            | V3            | V4            | EW          | Exacerbation visit ( $\le 2$ )  |

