| Protocol Activity   | Screen/Baseline | Study visit     |   |                 |   |   |
|---|-----------------|-----------------|---|-----------------|---|---|
|   |                 | X  | - | X  | - |   |
| Monthly CAT   | X  | -               | - | X  | - | - |
| Blood biomarkers (inclusive of serum sRAGE, CC16, IP-10, HbA1c) | X               | -               | - | X               | X | X |
| Sputum cytology                                    | X               | -               | - | X               | X | X |
| Sputum microbiome                                  | X               | -               | - | X               | X | X |

CAT=COPD assessment test, COPD=Chronic Obstructive Pulmonary Disease, HRCT=High-resolution computed tomography, EW=Early Withdrawal, EXACT=EXAceration of COPD Tool; SGRQ-C=St.George's Respiratory Questionnaire for COPD. CAPTURE=COPD Assessment in Primary Care to Identify Undiagnosed Respiratory Disease and Exacerbation Risk

1. Exacerbation visits only apply to subjects included in the Biomarker & Digital sub-cohort. Moderate exacerbations are defined as COPD exacerbations that require either systemic corticosteroids (intramuscular (IM), intravenous, or oral) and/or antibiotics. Severe exacerbations are defined as COPD exacerbations requiring hospitalization or result in death.
2. Informed consent must be conducted at the screen visit prior to performing any study procedures.
3. For COPD participants only;
4. When a trimonthly telephone interview overlaps a clinical visit, the COPD exacerbation assessment, COPD medication and treatment questionnaires will be completed at the clinic visit. A month is defined as 30 days in this study.
5. Data collection of COPD exacerbation assessment, COPD medication and treatment are not required for the healthy control participants.
6. CT scan should only be performed at withdrawal visit if the last study CT performed was more than a year ago. Inspiratory and expiratory HRCT scans are required at Visit 1 and Visit 4, while only inspiratory scan will be conducted on exacerbation visit. The CT scan for an exacerbation visit should only be performed if the last study CT scan performed was more than 14 days.
7. Pre-and post- bronchodilator values of spirometry test will be collected at each site visit.

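### The exacerbation imaging table puts 95% CIs on event records and names no allowance for two scans from the same patient

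*SAP*

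**What the plan says.** The rule is in SAP section 12 (Imaging Analysis), in the text after Table 3. It applies to COPD patients in the sub-cohort who had a CT at an exacerbation visit. The unit is explicit: "The analysis will be based on events (exacerbations) instead of on patients", and so "a same patient with 2 exacerbation imaging tests will be analysis as 2 records".

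On intervals: "Descriptive summary of baseline, exacerbation and the end of study (Visit 4 or early withdrawal) will be provided with 95% CI". Two changes, exacerbation minus baseline and end of study minus exacerbation, "will be provided in a same table with covariates of age, sex and height at baseline". Section 12 names no participant effect, repeated-measures covariance, clustered variance or resampling by patient.

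SAP section 2.4 sets the context. It says "This study is mainly descriptive with no formal inference associated with the study objectives", but also that "2-sided 95% confidence intervals will accompany all effect estimates".

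Protocol section 2 makes two exacerbation scans in one patient possible. On visits: "The total number of the exacerbation visits should be no more than 2, with an interval of at least 21 days". On scans (footnote 6 to the schedule): "The CT scan for an exacerbation visit should only be performed if the last study CT scan performed was more than 14 days".

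Three other places bear on the point:
- SAP section 8.1 specifies an unstructured within-subject covariance for the FEV1 and FVC repeated-measures models.
- The reporting and analysis plan appended to the SAP (section 7.4.1) planned a repeated-measures model for the HRCT changes. Section 12 does not carry it over.
- SAP Appendix 5 (section 17.5.1) averages multiple measurements at one analysis time point. Section 12 does not say whether it overrides that rule.

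**The concern.** A two-event patient has one baseline scan and one end-of-study scan. With the event as the record, each of those values enters its column twice and adds no information the second time. Both exacerbation-minus-baseline changes subtract the same baseline scan, and both end-of-study-minus-exacerbation changes use the same end-of-study scan. The records of such a patient are therefore positively correlated, and a CI that uses the number of records as its sample size overstates precision.

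The study plans no formal tests, so the interval is its main statement of uncertainty. This table also serves the objective of characterising exacerbation phenotypes through radiological features. The baseline and end-of-study means are weighted by event as well, so they describe the average exacerbation and not the average patient scanned. A reader could mistake one for the other.

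**Working it through.** **What the documents give.** The maximum is two exacerbation scans per patient (protocol section 2). The level is 95%, two-sided, z = 1.96 (SAP section 2.4). The planned sub-cohort contains 100 + 100 + 50 = 250 COPD participants, of whom 60 + 60 + 30 = 150 are to have an exacerbation history (protocol section 5.2). No N, SD, within-patient correlation or CI width is stated for this table, so there is no plan figure to reproduce.

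**What must be assumed.** The share f of scanned patients who have two exacerbation scans, and the within-patient correlation rho where the records are not exact duplicates. Both are shown as ranges.

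**Formula.** Take n patients, a share f with two records and the rest with one. The number of records is N = n(1 + f), and

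- true variance of the record mean = σ²[(1 − f)n + fn(2 + 2rho)] / N² = (σ²/N) × [1 + 2f·rho/(1 + f)]
- naive variance = σ²/N
- naive/true SE = 1/√[1 + 2f·rho/(1 + f)]
- coverage of the naive interval = 2Φ(1.96 × naive/true SE) − 1

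**Worked case, f = 0.2, rho = 1.** The bracket is 1 + 0.4/1.2 = 1.333, so naive/true SE = 1/1.155 = 0.87 and coverage is 91%. In units of σ²/n, the naive variance is 1/1.2 = 0.83 and the true variance is 1.6/1.44 = 1.11. Counting each patient once would give 1.00. Entering a scan twice thus makes the mean slightly less precise while the naive interval says it is more precise.

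**Correlation for each column.**
- *Baseline and end of study:* rho = 1, because the value is repeated.
- *Changes:* write baseline as u + e₀ and the two exacerbation scans as u + e₁ and u + e₂, with equal independent error variance s². The two changes have covariance s² and variance 2s², so rho = 0.5. If patients also differ in their response to exacerbation with variance τ², rho = (s² + τ²)/(2s² + τ²), which is 2/3 when τ = s. Taking 0.5 is therefore an assumption, and it rises if responses differ between patients. Age, sex and height do not absorb the shared scan error.
- *Exacerbation values:* rho is unknown. Over rho = 0.3 to 1, the correct width at f = 0.2 is 1.05 to 1.15 times the naive width.

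| f | rho = 1: bracket | naive/true SE | coverage | rho = 0.5: bracket | naive/true SE | coverage |
|---|---|---|---|---|---|---|
| 10% | 1.182 | 0.92 | 93% | 1.091 | 0.96 | 94% |
| 20% | 1.333 | 0.87 | 91% | 1.167 | 0.93 | 93% |
| 30% | 1.462 | 0.83 | 90% | 1.231 | 0.90 | 92% |
| 50% | 1.667 | 0.77 | 87% | 1.333 | 0.87 | 91% |
| 100% (upper bound) | 2.000 | 0.71 | 83% | 1.500 | 0.82 | 89% |

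**Check by simulation** (60 patients, 8,000 runs, t-interval over records, no patient-specific response). Coverage for baseline was 0.91, 0.87 and 0.83 at f = 20%, 50% and 100%. For the change from baseline it was 0.93, 0.91 and 0.89. Both agree with the formula.

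**The case against.** The strongest reply is that the SAP does not say the records are independent. It says that there are two of them and gives no variance method. The covariates imply that some model is intended for the changes, and that model might include a participant term. This stands as a limit on wording: a reader might infer that the plan declares independence, and it does not. It does not remove the point. Section 12 names no adjustment, and a descriptive interval over event records, computed as written, has no other evident basis. This is firmest for the baseline and end-of-study columns, where no model is implied.

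A second reply is that the event is a legitimate unit, openly chosen. That is right. Weighting by event is what an event average means, and pairing each event with its own baseline lets the unadjusted columns subtract when data are complete. The fault lies in the intervals and the labelling, not in the choice of unit.

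A third is that the consequence is small: one descriptive table, with no test, decision or sample size resting on it. That also stands. It limits the importance, but SAP section 2.4 still promises 95% intervals.

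**Conclusion.** The point holds conditionally. If any scanned patient has two exacerbation scans, the rule in section 12, followed as written, gives intervals that are too narrow. For f of 10% to 30%, coverage is about 93% to 90% in the duplicated columns and, with an assumed correlation of 0.5, about 94% to 92% for the changes. The correct interval is never more than √2 = 1.41 times the naive one, because no patient has more than two records. The effect is zero if nobody has two scans. The direction is certain for the duplicated columns and rests on positive within-patient correlation for the others. The size cannot be fixed from the documents, because neither f nor the correlation is given.

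Two stronger readings are not supported. The 83% coverage figure requires every scanned patient to have two scans and applies only to the duplicated baseline and end-of-study values; it is a bound, not an expectation. Nor can patients with two exacerbation scans be equated with frequent exacerbators. SAP section 13.1 defines that group by two or more events in the year before the study. Two study visits spread over 30 months are something else, and the cap of two visits gives patients with more events no additional weight.

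**What to change.** In SAP section 12:

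- Keep the event as the unit for the exacerbation and change columns. Compute their 95% CIs with participant-clustered (robust) SEs, or with a participant random effect where it can be estimated, and keep age, sex and height. Clustered SEs are the safer default: if most patients have one record, the random-effect variance may be poorly estimated for some of the Table 3 measures.
- Summarise baseline and end-of-study values once per patient, or keep them per event with participant-clustered CIs.
- Show the number of patients and the number of events for every column. If baseline and end of study are counted once per patient, denominators differ and column means no longer subtract to the mean change; a footnote should say so.
- State that section 12 overrides the averaging rule in section 17.5.1.

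The cost is a few lines of SAP wording, a clustered variance for each imaging measure and slightly wider intervals. No new data are needed.
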